11. CHANGES AND MODIFICATIONS TO THE ANALYSIS PLAN

All versions of the SAP are listed in [Table 9](#).

Table 9: Statistical Analysis Plan Versions

SAP Version	Date
Original	08 JAN 2021
Amendment 1	25 APR 2022
Amendment 2	11 SEP 2024

11.1. Changes to Protocol-Defined Analyses

In Section 9.5, QTcB and QTcF were collected by the sites and added to the analyses. In Appendix A, listings were added for both QTcB and QTcF.

11.2. Changes to the Statistical Analysis Plan

11.2.1. Amendment 1

- Section 5.4.1 was updated to clarify that participants with missing baseline assessments will be excluded from the ITT population for the responder analyses.
- In Section 7.1, the combination of DIPSS stratification levels at the time of interim analyses were added.
- In Section 7.3.1 and Section 7.4.2.2, the nonevaluable definitions for the primary endpoint analysis of spleen volume and secondary endpoint analysis of MFSAF TSS, respectively, were added.
- In Section 7.4.2, the window for deriving MFSAF TSS at Week 24 was modified to capture the assessments from the last week before participants return the device.
- Incorporation of administrative changes. Other minor, administrative changes and changes according to the Protocol Amendment 1 were incorporated throughout the SAP.

11.2.2. Amendment 2

- In Section 5, Section 7.3.3, Section 7.4, and Section 7.5, language was added to indicate that supportive, sensitivity analyses as well as some efficacy analyses with immature data will not be performed due to due to the early study termination.
- In Section 9, box-and-whisker plot was replaced by line plot for HGB, platelet counts, leukocytes, and neutrophils for readability.
- In Appendix A, numbers of the tables, figures, and listings were updated to keep them consistent with the numbering in the latest table, figure, and listing standard shells, and to align with updated data analysis based on the termination of the study. A shift table for bone marrow fibrosis was added to explore the treatment effect on the bone marrow fibrosis.
- Other, minor, administrative changes have been incorporated throughout the SAP.

APPENDIX A. PLANNED TABLES, FIGURES, AND LISTINGS

This appendix provides a list of the planned tables, figures, and listings for the CSR. Shells are provided in a separate document for tables that are not in the Standard Safety Tables v1.9.

The lists of tables, figures, and listings are to be used as guidelines. Modifications of the lists that do not otherwise affect the nature of the analysis will not warrant an amendment to the SAP.

Tables

Table No.	Title	Population	Standard
Baseline and Demographic Characteristics			
1.1 Disposition			
1.1.1	Analysis Populations	ITT	X
1.1.2	Summary of Participant Disposition	ITT	X
1.1.3	Summary of Number of Participants Enrolled by Country and Site	ITT	X
1.1.4	Summary of Protocol Deviations	ITT	X
1.2 Demography and Baseline Characteristics			
1.2.1	Summary of Demographics and Baseline Characteristics	ITT	X
1.3 Baseline Disease Characteristics			
1.3.1	Summary of Baseline Disease Characteristics	ITT	
1.3.2	Summary of Myelofibrosis History	ITT	
1.3.3	Summary of Myelofibrosis Screening Symptom Score	ITT	
1.3.4	Summary of Prior Systemic Cancer Therapy by WHO Drug Class and Preferred Term	ITT	X
1.4 Prior Medication and Concomitant Medication			
1.4.1	Summary of Prior Medications	ITT	X
1.4.2	Summary of Concomitant Medications	ITT	X
1.4.3	Summary of Prior Ruxolitinib History	ITT	
1.5+ Others			
1.5.1	Summary of General Medical History	ITT	X
Efficacy			
2.1 Primary Efficacy			
2.1.1.1	Cochran-Mantel-Haenszel Test of Proportion of Participants With $\geq 25\%$ Reduction in Spleen Volume at Week 12 and Week 24	ITT	
2.2 Secondary Efficacy			
2.2.1.4	Summary of Spleen Volume by Visit	ITT	
2.2.2.1	Cochran-Mantel-Haenszel Test of Proportion of Participants With $\geq 50\%$ Reduction in MFSAF v4.0 Total Symptom Score at Week 12 and Week 24	ITT	
2.2.2.3	Time to the First $\geq 50\%$ Reduction in MFSAF v4.0 Total Symptom Score	ITT	
2.2.2.4	Summary of MFSAF v4.0 Total Symptom Score Using 7-Day Window by Visit	ITT	
2.2.2.5.1	Summary of MFSAF v4.0 Individual Symptom Scores by Visit – Fatigue	ITT	
2.2.2.5.2	Summary of MFSAF v4.0 Individual Symptom Scores by Visit – Night Sweats	ITT	
2.2.2.5.3	Summary of MFSAF v4.0 Individual Symptom Scores by Visit – Itchiness	ITT	
2.2.2.5.4	Summary of MFSAF v4.0 Individual Symptom Scores by Visit – Abdominal Discomfort	ITT	
2.2.2.5.5	Summary of MFSAF v4.0 Individual Symptom Scores by Visit – Pain Under Left Ribs	ITT	
2.2.2.5.6	Summary of MFSAF v4.0 Individual Symptom Scores by Visit – Early Satiety	ITT	
2.2.2.5.7	Summary of MFSAF v4.0 Individual Symptom Scores by Visit – Bone Pain	ITT	
2.2.2.6	Summary of MFSAF v4.0 Spleen-Related Symptom Scores by Visit	ITT	

Table No.	Title	Population	Standard
2.2.3.1	Summary of Proportion of Participants With $\geq 25\%$ Reduction in Spleen Volume	ITT	
2.2.3.2	Summary of Response Categories for MFSAF v4.0 Total Symptom Score by Visit	ITT	

Safety			
3.1 Dose Exposure			
3.1.1	Summary of Exposure and Duration of Exposure to Parsaclisib/Placebo	Safety	X
3.1.2	Summary of Exposure and Duration of Exposure to Ruxolitinib	Safety	X
3.1.3	Summary of Parsaclisib Compliance	Safety	X
3.2 Adverse Events			
3.2.1	Overall Summary of Treatment-Emergent Adverse Events	Safety	X
3.2.2	Summary of Treatment-Emergent Adverse Events by MedDRA System Organ Class and Preferred Term	Safety	X
3.2.3	Summary of Treatment-Emergent Adverse Events by MedDRA Preferred Term in Decreasing Order of Frequency	Safety	X
3.2.5	Summary of Treatment-Emergent Adverse Events by MedDRA System Organ Class, Preferred Term, and CTCAE Grade Category	Safety	X

Table No.	Title	Population	Standard
3.2.6	Summary of Grade 3 or Higher Treatment-Emergent Adverse Events by MedDRA System Organ Class and Preferred Term	Safety	X
3.2.7	Summary of Grade 3 or Higher Treatment-Emergent Adverse Events by MedDRA Preferred Term in Decreasing Order of Frequency	Safety	X
3.2.8	Summary of Serious Treatment-Emergent Adverse Events by MedDRA System Organ Class and Preferred Term	Safety	X
3.2.9	Summary of Serious Treatment-Emergent Adverse Events by MedDRA Preferred Term in Decreasing Order of Frequency	Safety	X
3.2.10.1	Summary of Parsaclisib/Placebo Treatment-Related Treatment-Emergent Adverse Events by MedDRA System Organ Class and Preferred Term	Safety	X
3.2.10.2	Summary of Ruxolitinib Treatment-Related Treatment-Emergent Adverse Events by MedDRA System Organ Class and Preferred Term	Safety	X
3.2.10.3	Summary of Parsaclisib/Placebo/Ruxolitinib Treatment-Related Treatment-Emergent Adverse Events by MedDRA System Organ Class and Preferred Term	Safety	X
3.2.11.1	Summary of Parsaclisib/Placebo Treatment-Related Treatment-Emergent Adverse Events by MedDRA Preferred Term in Decreasing Order of Frequency	Safety	X
3.2.11.2	Summary of Ruxolitinib Treatment-Related Treatment-Emergent Adverse Events by MedDRA Preferred Term in Decreasing Order of Frequency	Safety	X
3.2.13.1	Summary of Parsaclisib/Placebo Treatment-Related Treatment-Emergent Adverse Events by MedDRA System Organ Class, Preferred Term, and CTCAE Grade Category	Safety	X
3.2.13.2	Summary of Ruxolitinib Treatment-Related Treatment-Emergent Adverse Events by MedDRA System Organ Class, Preferred Term, and CTCAE Grade Category	Safety	X
3.2.14.1	Summary of Grade 3 or Higher Parsaclisib/Placebo Treatment-Related Treatment-Emergent Adverse Events by MedDRA System Organ Class and Preferred Term	Safety	X
3.2.14.2	Summary of Grade 3 or Higher Ruxolitinib Treatment-Related Treatment-Emergent Adverse Events by MedDRA System Organ Class and Preferred Term	Safety	X
3.2.15.1	Summary of Parsaclisib/Placebo Treatment-Related Serious Treatment-Emergent Adverse Events by MedDRA System Organ Class and Preferred Term	Safety	X
3.2.15.2	Summary of Ruxolitinib Treatment-Related Serious Treatment-Emergent Adverse Events by MedDRA System Organ Class and Preferred Term	Safety	X
3.2.16	Summary of Treatment-Emergent Adverse Events With a Fatal Outcome by MedDRA System Organ Class and Preferred Term	Safety	X
3.2.18.1	Summary of Treatment-Emergent Adverse Events Leading to Parsaclisib/Placebo Dose Reduction by MedDRA System Organ Class and Preferred Term	Safety	X
3.2.18.2	Summary of Treatment-Emergent Adverse Events Leading to Ruxolitinib Dose Reduction by MedDRA System Organ Class and Preferred Term	Safety	X
3.2.19.1	Summary of Treatment-Emergent Adverse Events Leading to Parsaclisib/Placebo Dose Interruption by MedDRA System Organ Class and Preferred Term	Safety	X
3.2.19.2	Summary of Treatment-Emergent Adverse Events Leading to Ruxolitinib Dose Interruption by MedDRA System Organ Class and Preferred Term	Safety	X
3.2.20.1	Summary of Treatment-Emergent Adverse Events Leading to Discontinuation of Parsaclisib/Placebo by MedDRA System Organ Class and Preferred Term	Safety	X
3.2.20.2	Summary of Treatment-Emergent Adverse Events Leading to Discontinuation of Ruxolitinib by MedDRA System Organ Class and Preferred Term	Safety	X
3.2.22	Summary of Treatment-Emergent Adverse Events by MedDRA Preferred Term: Life-Table Method	Safety	X

Table No.	Title	Population	Standard
3.2.23	Summary of Treatment-Emergent Adverse Events by MedDRA System Organ Class and Preferred Term: Life-Table Method	Safety	X
3.2.24.1	Summary of Treatment-Emergent Adverse Events of Special Interest by MedDRA Preferred Term	Safety	X
3.2.24.2	Kaplan-Meier Estimates of Time to the First Onset of Treatment-Emergent Adverse Events of Special Interest by MedDRA Preferred Term	Safety	X
3.2.24.3	Kaplan-Meier Estimates of Longest Duration of Treatment-Emergent Adverse Events of Special Interest by MedDRA Preferred Term	Safety	X

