3. STUDY DESIGN

This is a Phase 3, randomized, double-blind study of the combination of the PI3K δ inhibitor parsaclisib or matching placebo and the JAK1/2 inhibitor ruxolitinib in participants with PMF or secondary MF (PPV-MF or PET-MF) who have had suboptimal response while receiving ruxolitinib monotherapy. Participants must meet Protocol-defined criteria for suboptimal response to ruxolitinib monotherapy. After participants have been determined to meet all criteria, they will be randomized to 1 of 2 treatment groups and will receive parsaclisib or matching placebo at a dose of 5 mg QD beginning on Day 1. Participants will also continue to receive the stable dose of ruxolitinib they were taking for the 8 weeks prior to Day 1. Both parsaclisib/matching placebo and ruxolitinib dosing will continue for the duration of participation in the study. [Figure 1](#) presents the study design schema.

Figure 1: Study Design Schema

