5.2. Treatment Groups

This is a randomized, double-blind, parallel treatment group design. Participants will be summarized by treatment group. A participant randomized to the control group may make a crossover to the active treatment prior to Week 24 if the participant meets the criteria for an early crossover. Unless specified, efficacy and safety analyses for between-treatment comparisons (parsaclisib + ruxolitinib vs placebo + ruxolitinib) will be conducted using the data truncated at the time of treatment crossover for those participants who made an early treatment crossover prior to Week 24. Data collected after the treatment crossover will be summarized and tabulated separately without treatment comparisons.

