9.1. General Considerations

The safety analyses, including frequency and severity of AEs and SAEs and mean change and percentage change in vital signs, ECGs, and lab parameters, will be summarized by treatment group in the safety population.

Summary tables may be replaced with listings when appropriate. For instance, an AE frequency table may be replaced with a listing if it only contains a few unique PTs reported on relatively few participants.

Safety analyses for treatment comparisons will exclude data collected after treatment crossover. Data post-treatment crossover will be analyzed separately and descriptively without any treatment comparisons. Day 1 of crossover will be used for the crossover participants in the crossover phase.

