9.2.2. Adverse Events of Special Interest

The following TEAEs, regardless of seriousness, will be tabulated by MedDRA PT for the safety population for each treatment group.

- Colitis
- Diarrhea of Grade 2 or higher
- Rash of Grade 2 or higher
- Pneumonitis
- Dermatitis exfoliative
- Intestinal perforation
- Cytomegalovirus infection
- Herpes simplex infection, including oral herpes and genital herpes as AE terms
- Herpes (varicella) zoster virus infection, including herpes zoster, shingles, and VZV as AE terms
- Pneumocystis jirovecii infection
- ALT increased $\geq 5 \times$ ULN
- AST increased $\geq 5 \times$ ULN

Adverse events of special interest should be captured in the eCRF.

The time to onset of the first occurrence of each AESI will be analyzed using the KM method. Median time to onset of the first occurrence of each AESI will be estimated by the KM method. Participants with no AESI at the time of analysis will be censored at the time of analysis.

The longest duration of AESI will be analyzed using the KM method for participants in the safety population with at least 1 occurrence of the AESI. The median longest duration of each AESI will be estimated by the KM method. Participants whose AESI was not resolved at the time of analysis will be censored at the time of the analysis. Participants with nonserious TEAEs not resolved by 35 days after the end-of-treatment visit will be censored at 35 days after the end-of-treatment visit.

Two consecutive AESIs with different toxicity grades but with the start date of the later AESI overlapped with the end date of the previous AESI are considered as 1 AESI in calculating the duration of AESI.

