- Summary of parsaclisib/placebo treatment-related serious TEAEs by MedDRA SOC and PT
- Summary of ruxolitinib treatment-related serious TEAEs by MedDRA SOC and PT
- Summary of TEAEs with a fatal outcome by MedDRA SOC and PT
- Summary of TEAEs leading to parsaclisib/placebo dose reduction by MedDRA SOC and PT
- Summary of TEAEs leading to ruxolitinib dose reduction by MedDRA SOC and PT
- Summary of TEAEs leading to parsaclisib/placebo dose interruption by MedDRA SOC and PT

- Summary of TEAEs leading to ruxolitinib dose interruption by MedDRA SOC and PT
- Summary of TEAEs leading to discontinuation of parsaclisib/placebo by MedDRA SOC and PT
- Summary of TEAEs leading to discontinuation of ruxolitinib by MedDRA SOC and PT
- Summary of TEAEs by MedDRA PT: life-table method
- Summary of TEAEs by MedDRA SOC and PT: life-table method
- Summary of treatment-emergent AESIs by MedDRA PT
- Median time to the first onset of treatment-emergent AESIs by MedDRA PT
- Median longest duration of treatment-emergent AESIs by MedDRA PT

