4.3 Adverse Events	
4.3.1	Kaplan-Meier Estimates of Time to the First Onset of Treatment-Emergent Adverse Events of Special Interest by MedDRA Preferred Term
4.3.2	Kaplan-Meier Estimates of Duration of Treatment-Emergent Adverse Events of Special Interest by MedDRA Preferred Term

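### AESI duration is planned only as each participant's longest episode, which grows with observation time, and the crossover cut can shorten that time only on placebo; first-episode duration and episode counts should stand beside it

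*SAP*

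**What the plan says.** Section 9.2.2 gives one definition of AESI duration: "The longest duration of AESI will be analyzed using the KM method for participants in the safety population with at least 1 occurrence" of the event. Section 9.2.3 lists the matching summary, "Median longest duration of treatment-emergent AESIs by MedDRA PT", and Appendix A Table 3.2.24.3 carries the same wording, "Kaplan-Meier Estimates of Longest Duration of Treatment-Emergent Adverse Events of Special Interest by MedDRA Preferred Term". Figure 4.3.2 is titled "Kaplan-Meier Estimates of Duration of Treatment-Emergent Adverse Events of Special Interest by MedDRA Preferred Term", without the word longest. No section defines a first-episode or per-episode duration.

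Section 9.2.2 joins consecutive AESIs into one only when they overlap and differ in grade. Separate recurrences stay separate, so the longest is picked from a variable number of episodes. An unresolved AESI is censored at the time of analysis, and a nonserious one at 35 days after the end-of-treatment visit. Crossover is not mentioned.

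Three other statements set how long each group is observed:
- Section 5.2: "A participant randomized to the control group may make a crossover to the active treatment prior to Week 24", if the early-crossover criteria are met.
- Section 9.1: "Safety analyses for treatment comparisons will exclude data collected after treatment crossover".
- Section 3: "Both parsaclisib/matching placebo and ruxolitinib dosing will continue for the duration of participation in the study".

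**The concern.** A maximum over episodes depends on how many episodes were seen, and that depends on how long the participant was watched. KM censoring handles an episode still open at the cut. It cannot restore later episodes that would have started after the cut, so it does not correct a maximum taken over fewer of them.

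Under 5.2 and 9.1 the crossover cut falls only on placebo. For AESIs that can recur, such as diarrhea, rash or herpes infections, the table could show a longer duration on parsaclisib when the episodes themselves last equally long. The statistic also mixes how often an event recurs with how long it lasts, and no other planned output gives the length of an episode.

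**Working it through.** The SAP states no figure for AESI duration, so there is none to reproduce. The check asks how far the planned statistic moves when the true episode length is the same in both groups.

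**Inputs from the SAP.** Longest episode among participants with at least 1 occurrence (9.2.2); crossover for control only (5.2); post-crossover data excluded from comparisons (9.1).

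**Assumptions, not in the SAP.** Exponential episode lengths with mean 14 days (median 14 × ln 2 = 9.7 days) in both groups; Poisson recurrence at 0.5 to 4 episodes a year; 48 weeks of observation, cut to 24 weeks for placebo participants who cross; share crossing 25%, 50% or 100%.

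**Formula.** Let Λ = rate × weeks / 52 and S(t) = exp(−t/14). Among participants with at least one episode,

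P(longest ≤ t) = [exp(−Λ·S(t)) − exp(−Λ)] / [1 − exp(−Λ)].

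Setting this to 0.5 gives S = −ln[(1 + exp(−Λ))/2] / Λ and a median of −14·ln S.

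**Worked case, 1 episode a year, all placebo participants crossing.**
- 24 weeks: Λ = 0.4615, S = 0.4428, median = 11.4 days.
- 48 weeks: Λ = 0.9231, S = 0.3885, median = 13.2 days.
- Ratio = 13.24 / 11.40 = 1.16.

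**Partial crossover.** With share p cut at 24 weeks, the numerator and denominator above become sums over the two observation times, weighted p and 1 − p, and the median is solved numerically. Entries are the placebo median in days, with the excess of the parsaclisib median in brackets (percentages from unrounded medians).

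| Episodes/year | Parsaclisib, 48 weeks | Placebo, 25% cross | Placebo, 50% cross | Placebo, 100% cross |
|---|---|---|---|---|
| 0.5 | 11.4 | 11.3 (+1.2%) | 11.1 (+2.9%) | 10.5 (+8.3%) |
| 1 | 13.2 | 12.9 (+2.5%) | 12.5 (+5.7%) | 11.4 (+16.1%) |
| 2 | 17.0 | 16.3 (+4.6%) | 15.4 (+10.4%) | 13.2 (+28.7%) |
| 4 | 23.9 | 22.4 (+6.6%) | 20.8 (+15.1%) | 17.0 (+40.4%) |

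**Check with KM censoring at the cut.** The formula ignores episodes still open at the cut. A simulation that censored them and took the KM median (30,000 participants per cell, median episode 14 days) gave, at 24 against 48 weeks:
- 1 episode a year: 16.3 vs 18.7 days
- 2 a year: 18.2 vs 23.7 days
- 4 a year: 22.6 vs 31.4 days

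These are ratios of about 1.15, 1.30 and 1.39, so KM does not remove the effect. With the first episode instead of the longest, the KM median stayed between 13.8 and 14.5 days (true value 14) at every rate from 0.5 to 4 a year and every observation time from 12 to 96 weeks.

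**Recurrence alone.** At 48 weeks for everyone, raising the rate from 1 to 4 a year moves the simulated median longest duration from 18.7 to 31.4 days with episode length unchanged.

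**The case against.** The longest episode is a recognised worst-case safety summary. It is labelled as such in 9.2.2, 9.2.3 and the table, is marked as a sponsor standard, and has no test attached. Incidence (Table 3.2.24.1) and time to first onset (Table 3.2.24.2) are shown separately. This stands, and it is why the statistic should be kept.

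Several stronger readings are tempting, and the SAP does not support them.
- A reader might take +16% to +40% as the expected distortion. That needs every placebo participant to be cut at Week 24. Crossover is optional and, before Week 24, tied to criteria, and the SAP gives no crossover share.
- A reader might conclude that parsaclisib will look worse overall. Only the crossover cut is shown to be one-sided. Observation also depends on discontinuation in each group, which the SAP does not give.
- A reader might call a rise caused by more frequent episodes on drug a bias. More recurrence is a real treatment effect; the difficulty is only that this output cannot separate it from episode length.
- A reader might hold that Figure 4.3.2 shows a different quantity. The text defines only one AESI duration, and Appendix A calls its lists guidelines, so the title is most likely a shortened label.

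The affected events are also limited. The table is by preferred term, so the same term must recur, and events such as intestinal perforation or pneumonitis are unlikely to do so at these rates. With few affected participants, sampling error dominates: assuming 10 of them with one exponential episode each of mean 14 days, the sample median has a 95% range of about 3.8 to 20.4 days. The shifts for 25% crossing at 1 to 4 episodes a year are only 0.3 to 1.5 days.

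What remains is that the plan's own crossover rule makes the one planned duration comparison depend on unequal observation, and KM does not repair this.

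**Conclusion.** The point holds as a minor one. For AESIs that recur, the by-group comparison of longest duration can be distorted by the placebo-only crossover cut when episode lengths are equal. Under the stated assumptions and 1 to 4 episodes a year, the excess on parsaclisib is about 2.5% to 7%, 6% to 15%, or 16% to 40% for 25%, 50% or 100% crossing at Week 24. At 0.5 episodes a year it is at most about 8%, and for events that occur once it is nil. Episode rate, episode length, crossover share and follow-up are all assumptions, so the SAP fixes the mechanism but not the size.

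Sections 9.1 and 9.2.2 also need reconciling. The first excludes post-crossover data, while the second censors unresolved AESIs at the time of analysis without mentioning crossover. The output is descriptive and the study ended early, so no efficacy conclusion and no formal test is affected.

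**What to change.** 1. In 9.2.2, 9.2.3 and Table 3.2.24.3, keep the longest duration as the labelled worst-case summary. Beside it, by treatment group, add the KM duration of the first episode of each AESI and the number of episodes per participant.
2. In 9.2.2, state that a placebo participant's unresolved AESI is censored at crossover in the between-group comparison, so that it agrees with 9.1.
3. Give Figure 4.3.2 the same quantity name as the table. This is editorial.

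The cost is SAP wording, one derived variable from adverse event records already held, and the added columns. First-episode duration alone would miss a prolonged later episode, so it should be added to the longest duration and not replace it.

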3.3 Laboratory			
3.3.1.1	Summary of Laboratory Values - Hematology	Safety	X
3.3.1.2	Summary of Laboratory Values - Chemistry	Safety	X
3.3.1.3	Summary of Laboratory Values - Coagulation	Safety	X
3.3.3.1	Shift Summary of Hematology Laboratory Values in CTC Grade - to the Worst Abnormal Value	Safety	X
3.3.3.2	Shift Summary of Chemistry Laboratory Values in CTC Grade - to the Worst Abnormal Value	Safety	X
3.3.3.3	Shift Summary of Coagulation Laboratory Values in CTC Grade - to the Worst Abnormal Value	Safety	X
3.3.3.4	Treatment-Emergent Worsening of Laboratory Abnormalities - Hematology	Safety	X
3.3.3.5	Treatment-Emergent Worsening of Laboratory Abnormalities - Chemistry	Safety	X
3.3.3.6	Treatment-Emergent Worsening of Laboratory Abnormalities - Coagulation	Safety	X
3.3.4.1	Summary of Participants With Elevations in Liver Chemistry Tests	Safety	X
